The feasibility of the TEHE plus program includes the evaluation of the recruitment and retention, acceptability, compliance, and delivery of the intervention. This study aims to measure the feasibility of the TEHE groups (including all five intervention arms). In the data collection process, the eligible participants recruited patients, a number of participants completing the intervention program will be recorded. Adherence to the intervention will be assessed using data collected from the activity tracker on minutes of moderate-intensity or greater activity. During the weekly exercise training, participants will discuss their home-based exercise barriers and potential solutions. At the end of the 12 weeks, participants will answer open-ended questions about their satisfaction and opinion about the programs (intervention groups) and the use of physical activity trackers and mobile phone application (control group).

By participating in the study, participants will spend 12 weeks, with 2 study visits. Participants will continue to receive their routine care and current therapy. They will continue with their therapy when the study ends or if the participation end prematurely. During the study, unexpected circumstances (e.g., worsening of cancer, extreme anemia, or another late side effect of cancer treatment). Participants will be removed from the study if his/her disease and/or condition is worsening.

Participants' personal information will be kept as private as possible and participants' names will not appear on any of the data forms. Blood sample tubes will be coded but de-identified and will be stored in locked freezers at Johns Hopkins School of Nursing biophysiological laboratory freezer until analyzed. Participants' health information will only be disclosed for this research study. Data will be stored for five years using assigned codes and will be kept on a password-protected computer held at the Johns Hopkins School of Nursing. Only study investigators will have access to the study data. After five years, the data will be shredded and discarded.

5. Inclusion/Exclusion Criteria

Exercise study:

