The mean and standard deviation of each outcome measure, recruitment rate, drop out, acceptability, tolerability will be calculated per group per study visit. The study primary aim the feasibility of a 12-week technology-enhanced home exercise (TEHE) program and TEHE plus program (***Aim 1***) will be analyzed using descriptive statistics of eligible participants and recruited participants, a number of participants completing the intervention program, compliance (number of participants complete the daily step goal), and participants' satisfaction and opinion of the intervention. To examine the effect of the TEHE program on fatigue, physical activity and serum biomarkers (Heat Shock Protein 90 and Brain-Derived Neurotrophic Factor) (***Aim 2***), the paired t-test will be used to analyze the effect of the program on fatigue, PA and biomarkers at the end of the program compared to baseline. The student t-test will be used to compare the variables among participants in the TEHE program, Acupressure only, TEHEplus, and TEHE +MBI compare to the usual care (control) group.

The secondary aims: The change of fatigue and physical activity level in week 12 compared to baseline will be calculated. Analysis of Variance (ANOVA) will be used to compare the effect of the TEHEplus, combined TEHE, and MBI with the TEHE only and Acupressure only on fatigue and physical activity (***Aim 3***). Change from baseline to 12 weeks will be computed for serum HSP90AA1 and BDNF levels. ANOVA will be used to examine the differences of change in serum biomarkers at week 12 compared to baseline in the TEHE only, Acupressure only, TEHEplus, TEHE +MBI and control (usual care) groups (***Aim 4***).

Sample size justification

Sufficient information from prior studies is not available for us to conduct a sample size calculation for the proposed multilevel analyses. The purpose of this pilot project is to explore the feasibility of the program and the relationships between the trajectories of the outcome measures, and not to achieve high power. The proposed N of 110 (22 participants/group) will likely result in low (below 0.60) statistical power. Results obtained will inform future power analyses for full-scale studies.

Early stopping criterion for safety/futility/efficacy as needed.

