The purpose of this pilot study is to examine the feasibility of the interventions. Therefore, participants may be asked to stop their participation early if there are serious complications include metastasis of the disease is found, serious injuries (broken bone, severe muscle injury) that prohibit the participants to exercise, severe infection during the 12 weeks intervention (e.g., fever, redness, swelling, etc.).

Inclusion and exclusion criterion: please see section 5.

Intervention/Independent Variables.

Technology-Enhanced Home Exercise (TEHE) Program: An online individual exercise session will be offered at the first study visit. Participants will be complete an exercise training program (45-60 min) to reach a moderate intensity using the heart rate monitor and exertion level.

The online exercise training/consultation program will include

- Goal setting/discussion of the progress (25 min): Participants will spend 25 min to discuss the physical activity barriers and set up a goal for the program.
- Exercise safety and body alignment (10 min): Participants will learning about posturing and body alignment to maintain their safety during exercise and monitoring the heart rate using the wearable device.
- Review physical activity and symptoms (15 min)
- At the end of the program, participants will select follow up methods (phone or video call), reminder message scheduled time and frequency.

At home: Participants will receive a weekly recommendation through a smartphone application and be instructed to follow their physical activity/step goals. Participants will receive a summary report of their weekly physical activity and symptoms (Fitbit and mobile phone application data).

The PI ([name]) will monitor the intervention session to ensure intervention fidelity. Adherence to the intervention will be assessed by data collected from the activity tracker on minutes of moderate-intensity or greater activity. At the end of the 12 weeks, participants will answer open-ended questions about their satisfaction with the program.

The Acupressure program: Participants in this group will receive online or in person auricular point acupressure (APA) and body pressure points training at the first study visit. An online educational video and written material developed by interventionists and PI, will

Figure 3. Ear Points for Fatigue

Date: September 26, 2024

Principal Investigator: [name]

Application Number: IRB00154198

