At home: Participants will be received a weekly recommendation for points that tailored for their weekly symptoms experience and instructed to press the tape and seeds covering each ear point for 10 seconds per time for 3 times/point four times daily (morning, afternoon, evening and before bed), even when they do not experience fatigue. The optimal pressure is considered to have been achieved when the participants feel localized tingling or mild discomfort. The tape and seeds will remain on ear points for 5 days. Participants will be instructed to remove both at the end of the 5th day and apply the new seeds.

To ensure the accuracy of the ear points, participants will be asked to send the photo of their ear after the seeds are placed for comments and suggestions.

The combined Acupressure and TEHE program (TEHE plus): In addition to the TEHE program, participants will receive Acupressure training at the first study visit and weekly recommendations that include both exercise goal and suggested pressure points.

The combined MBI and TEHE program: In addition to the TEHE program, the TEHE+MBI group will receive a 10-15 min audio-recording of a mindfulness-based body scan or mindful movement or mindful breathing. This technique is often used as an entry point to mindfulness

meditation.^{45, 46} This recording guided the participants to focus on specific bodily and breathing sensations.

At home: Participants will be instructed to include mindfulness-based body scan or mindful breathing, mindful movement. The participant will be instructed to acknowledge all sensation with the non-judgemental acceptance and not attempting to change the experience. Participants will receive a weekly recommendation for the activity goals and suggested mindfulness techniques.

Control Group: The control group will receive instructions on how to use the physical activity tracker and the smartphone application. Participants will be asked to meet with a research team member on the first week to review the equipment set up instruction. Participants will be asked to monitor their physical activity daily using Fitbit and receive a daily notification to complete the short on fatigue and other symptoms from the smartphone application.

Dependent variables and instruments. The study variables will be measured as follows:

Questionnaires

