Potential Risks and Protection Against Risks. Potential risks include (1) complications during the blood draw including pain and bleeding at the drawing site, (2) complications of the APA procedure, (3) minimum discomfort might occur while wearing the Fitbit charge (worn like a bracelet), (4) complications such as fainting or injury during the exercise program may occur. The MBI and responding to the questionnaires has no medical risk. The PI and research team plan to prevent the following risks:

1. Complications during the blood draw. Participants may experience pain and discomfort during the blood draw. They may also be at risk of bleeding. All blood draws will be performed by a certified phlebotomist. After the blood draw, participants' conditions will be monitored by a registered nurse (RN).
2. Complications of APA procedure: The auricular acupuncture procedure is considered safe with minimal risk. The most frequently reported adverse events were local skin irritation and discomfort, mild tenderness or pain, and dizziness. These events were transient, mild, and tolerable. Participants will be instructed to remove the tap with the seed when adverse events occur.
3. Minimum discomfort might occur while wearing the Fitbit charge (worn like a bracelet). Participants will be asked to wear a Fitbit to measure physical activity and sleep duration during their participation in the study. Participants will be instructed to take the band off when taking a shower. This equipment may cause discomfort. The material does not contain latex; however, the clasp is made of surgical grade stainless steel and contains traces of nickel, which may cause a rash. The device can be easily removed if discomfort is experienced. Participants will be asked to record the time and reason when and why they removed the band.
4. Complications (e.g., fainting, injury) during the exercise program. Participants will be instructed to walk and exercise at their own pace in the safety of their environment. All participants will be instructed to wear tennis shoes, comfortable clothing, and to eat a light snack before exercise.

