activity and fatigue; (2) explore the effect of the combined TEHE program with Acupressure and MBI on fatigue and physical activity; and (3) determine the effectiveness of the TEHE alone, TEHEplus, and MBI+TEHE programs on serum biomarkers (Heat Shock Protein 90 and Brain-Derived Neurotrophic Factor) compare to control (usual care) group. A Safety Monitoring Committee (SMC) will be formed, consisting of Johns Hopkins University clinician faculty members who are independent of this proposed feasibility study. The SMC will be responsible for overall monitoring of the safety of participants in this proposed study and overseeing the PI, Co-Is, and research assistant.

The PI will be responsible for managing all data, securing privacy and confidentiality, minimizing and identifying risks, monitoring and reporting adverse events or any safety issues, and complying with timely reporting requirements to all applicable regulatory bodies for any adverse events or unexpected problems. Monthly reports will be completed by the PI detailing participant demographics, recruitment status, treatment retention rates, protocol compliance, data gathered and accuracy, and quality assurance or regulatory issues that transpired, and summary of any adverse events. The research team (PI, Co-Is, and research assistant) will meet weekly via face to face or conference calling to discuss data and safety monitoring.

The SMC will meet annually (or more frequently if needed) and review the annual reports completed by the PI; review study safety, integrity, and progress including any adverse events; provide advice about continuing, changing, or terminating the study when necessary; require more frequent reporting as needed; audit the study for compliance and verify the authenticity of data, and assess that the research team is complying with informed consenting and other required regulations. These annual meetings will be conducted face-to-face or through conference calls.

References

1. National Cancer Institute. SEER Stat Fact Sheets: Prostate Cancer. 2007-2011. <http://seer.cancer.gov/statfacts/html/prost.html>; 2014.

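### Tolerability is summarised per group and adverse events go to the safety committee, but no harm question is common to all five arms and described staff contact is greater in the active arms

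*Combined protocol and SAP*

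**What the plan says.** All places are in the combined protocol and SAP.

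- **Summary by arm.** Section 7, Analysis plan: "The mean and standard deviation of each outcome measure, recruitment rate, drop out, acceptability, tolerability will be calculated per group per study visit". Tolerability is not defined there or elsewhere.
- **Safety reporting.** Section 12 has the principal investigator write monthly reports that include a "summary of any adverse events". The safety committee reviews adverse events at least annually. Neither is stated to be broken down by arm.
- **Visits.** Section 4: "By participating in the study, participants will spend 12 weeks, with 2 study visits". This is the same in every arm.
- **Exercise arms.** Section 4: "During the weekly exercise training, participants will discuss their home-based exercise barriers and potential solutions". Section 7, on the TEHE programme, adds that "participants will select follow up methods (phone or video call), reminder message scheduled time and frequency".
- **Acupressure arms.** Section 7 says that, to check placement, "participants will be asked to send the photo of their ear after the seeds are placed for comments and suggestions".
- **Control.** Section 7, Control Group: "Participants will be asked to meet with a research team member on the first week to review the equipment set up instruction". After that the text describes daily Fitbit monitoring and a daily app prompt about fatigue and other symptoms.
- **Payment.** Section 10 lists phone or video follow-up among the things participants complete, without restricting it to any arm.

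**The concern.** If nobody asks about harms in a fixed way, events become known when a participant happens to mention them to staff. The more often staff and participant are in touch, the more events are recorded. Falls, muscle pain, dizziness and fainting can occur under usual care as well as during exercise or acupressure. An arm with little contact may therefore look safer only because fewer of its events are heard of.

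The trial compares four interventions with usual care, so per-group tolerability figures will be read side by side even without a formal test. Section 7 (Sample size justification) says that the results will inform full-scale studies. An apparent excess of harms in the exercise or acupressure arms, created by contact frequency, could carry over into that planning. Safety oversight is affected too, because events in the less-contacted arm may not reach the committee.

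**Working it through.** **Step 1: is there a common harm question?** I looked for any instrument, form or schedule that asks every arm about adverse events.

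- Table 1 appears in section 4 and again in section 7. Neither version has an adverse-event row.
- Section 4 has all participants answer the mEMA app daily for 12 weeks. Its content is described as fatigue level (section 8) or fatigue and other symptoms (section 7). Nothing says that it asks about injury, falls or fainting, or that an answer triggers an adverse-event report.
- The week-12 open questions differ by arm. Under section 4, intervention arms are asked about their programme and controls about the tracker and app.
- Section 8 tells acupressure participants what to do with the tape if an adverse event occurs. It does not tell them to inform staff.
- Randomisation follows the baseline assessments, so a per-visit tolerability figure can only be informative at study visit 2, where no harm item is scheduled.

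**Step 2: contact between visits, as the arm texts give it.**

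| Arm | Staff contact described between visits 1 and 2 |
|---|---|
| TEHE only | Weekly training discussion (section 4); phone or video follow-up (sections 4 and 7) |
| MBI+TEHE | As TEHE only |
| TEHEplus | As TEHE only, plus ear-photo feedback (section 7) |
| Acupressure only | Ear-photo feedback (section 7); no calls described |
| Control | One meeting in week 1 (section 7); no calls described |

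Two conflicts sit behind this table. Section 4 speaks of weekly training, while the programme text in section 7 describes one session at the first visit. Section 10 mentions follow-up calls for participants in general. No frequency or adverse-event content is given for any call.

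**Step 3: what unequal capture could do.** The plan gives no harm rate or capture rate, so it has no figure to reproduce on this point. The only design input is the group size: 5 × 22 = 110, as in the Sample size justification. (The abstract gives 105, which is 21 per group; the difference hardly matters here.) Everything else below is assumed.

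Let p be a true risk equal in both arms, with capture 0.9 in an active arm and s in control.

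- Recorded risks: a = 0.9p and c = s × p
- Apparent ratio: a/c = 0.9/s, which does not depend on p
- Standard error of the difference: √[a(1−a)/22 + c(1−c)/22]

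| p | s | a | c | Difference (points) | Ratio | SE (points) |
|---|---|---|---|---|---|---|
| 10% | 0.7 | 9% | 7% | 2 | 1.29 | 8.2 |
| 10% | 0.5 | 9% | 5% | 4 | 1.80 | 7.7 |
| 20% | 0.7 | 18% | 14% | 4 | 1.29 | 11.0 |
| 20% | 0.5 | 18% | 10% | 8 | 1.80 | 10.4 |
| 30% | 0.7 | 27% | 21% | 6 | 1.29 | 12.8 |
| 30% | 0.5 | 27% | 15% | 12 | 1.80 | 12.1 |

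With equal capture the difference is 0 and the ratio 1. In the worst row the distortion is 12/12.1, about one standard error.

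**The case against.** The strongest reply is that there is no harm comparison to distort. The quoted sentence is a descriptive summary alongside recruitment and drop-out, at two visits common to all arms. The t-tests and ANOVA are described for fatigue, physical activity and biomarkers. The adverse-event summary in section 12 is not stated to be by arm, and reading tolerability as adverse-event rates is an inference. Control participants also report symptoms daily through the same app, and PROMIS pain measures are taken in every arm at both visits. The active arms' contacts are not safety contacts either: ear photos serve to check placement, and the calls have no stated timing.

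Much of this stands. It rules out a claim that a planned test is biased, and it shows that some symptom data are collected equally. It does not supply a common harm question: symptom and pain scores are outcomes and are not stated to record events. That the contacts are incidental is the difficulty, because incidental contact is then the main way for an event to surface.

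A reader might go further in two ways that the documents do not support.

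- **That staff contact between visits exists only in the active arms.** Section 10 mentions calls without naming arms, so the imbalance is what the arm texts describe and is not established beyond them.
- **That the mindfulness arm will show fewer harms because section 8 says "The MBI and responding to the questionnaires has no medical risk".** That arm also receives the TEHE programme, whose risks section 8 lists, and section 12 covers any adverse event whatever its cause.

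**Conclusion.** The point holds as a risk of unequal ascertainment. Harms have no collection method common to the arms, and the contact through which they would otherwise surface is, as described, greater in the active arms. The likely direction is that active arms look worse than usual care; Acupressure only, with no described calls, may also differ from the exercise arms.

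The size cannot be computed from the documents. The ratios of 1.29 and 1.80 restate the assumed capture rates and show only what such rates would produce. At 22 per group the distortion would not exceed about one standard error over the range shown, so a false significant finding is not the main worry. A reader might also take the weeks without described contact in the control arm as the share of events missed. That does not follow, because events can be recalled at study visit 2.

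The conclusion rests on the arm texts being what is carried out. If calls in fact reach all arms equally, most of the imbalance disappears, but the lack of a common harm question remains. The point is worth acting on because the remedy is cheap.

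**What to change.** 1. Define tolerability and adverse event in section 7.
2. Add one identical yes/no harm item, with free text, to the mEMA survey in all five arms at a fixed interval, for example weekly.
3. Ask the same adverse-event checklist at study visit 2 in every arm, and add an adverse-event row to both copies of Table 1.
4. Base the per-group tolerability and adverse-event summaries on these common items. List events learned through calls, training or ear photos separately by source, and keep them for safety oversight.
5. Reconcile section 10 with the arm descriptions in sections 4 and 7: state whether follow-up calls apply to control and to Acupressure only, and whether exercise training is weekly or a single session.

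Cost: an IRB amendment, slight participant burden, and more minor events recorded in every arm. A weekly item would give at most 110 × 12 = 1,320 responses, so existing staff would need some time to review them. No extra visits are needed.

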Methods: Participants who meet the inclusion criteria will be randomly assigned to the TEHE only or Acupressure only or combined acupressure and TEHE (TEHE plus) or combined MBI and TEHE or control (usual care) group. All exercise groups will be offered a 12-week exercise program. They will be instructed to exercise at home to achieve weekly activity/step goals. Activity/steps and symptoms will be monitored daily using the FitBit and a smart phone application. Weekly summary report of physical activity and symptoms will be sent to participants through a web-based mobile phone application. In addition to the TEHE, the TEHEplus group will receive instructions on how to locate and apply the pressure on the acupressure points and weekly recommendation for acupressure points. The acupressure only group will receive only instruction on how to apply the pressure on the acupressure points through the online training or in person training with weekly recommendation for acupressure points. The MBI+TEHE group will receive a weekly recommendation to add mindfulness based intervention including body scan mindful breathing, and mindful movement. The control (usual care) group will report their symptoms level and monitor physical activity through Fitbit and smartphone application daily. At the end of week 12, in addition to the questionnaires, participants will answer open-ended questions about their opinions on the program. Symptoms will be assessed and blood will be drawn before and after the program. Participants who enrolled in the sub-study will be scheduled for one visit for an MRS.

2. Objectives (include all primary and secondary objectives)

Purpose/Specific Aims:

The study primary aims are to (1) test the feasibility of a 12-week technology-enhanced home exercise (TEHE) program and combined technology-enhanced home exercise and Acupressure (TEHEplus) program among cancer survivors; (2) to determine the effect of the TEHE plus program on fatigue, physical activity and serum biomarkers (Heat Shock Protein 90 and Brain-Derived Neurotrophic Factor) compared to the control (usual care) group.

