The feasibility of the TEHE plus program includes the evaluation of the recruitment and retention, acceptability, compliance, and delivery of the intervention. This study aims to measure the feasibility of the TEHE groups (including all three intervention arms). In the data collection process, the eligible participants recruited patients, a number of participants completing the intervention program will be recorded. Compliance with the intervention will be assessed using data collected from the activity tracker on minutes of moderate-intensity or greater activity. At the end of the program (12 weeks), participants will be asked to complete open questions on their satisfaction and opinion on the intervention and delivery method.

Primary and secondary objectives

The study primary aims are to (1) test the feasibility of a 12-week technology-enhanced home exercise (TEHE) program and combined technology-enhanced home exercise and Acupressure (TEHE plus) program among cancer survivors; (2) the effect of the TEHE program and TEHE plus on fatigue, physical activity and serum biomarkers (Heat Shock Protein 90 and Brain-Derived Neurotrophic Factor) compare to the control (usual care) group.

The secondary aims are (3) compare the effect of the TEHE only, Acupressure only, TEHEplus, and combined TEHE and MBI on fatigue and physical activity; and (4) determine the change in serum biomarkers at week 12 compared to baseline in the TEHE only, Acupressure only, TEHEplus, MBI+TEHE, and control (usual care) groups

Analysis plan

Exercise study:

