be provided. The participants will review the instruction video. During the online study visit, participants will be asked to locate the ear point, place the seed on the ear points, and pressing the ear points.

The training information will include

- 1) The selection of the ear point: The points that will receive acupressure include *sympathetic, nervous subcortex, Sanjian, kidney, liver, spleen, mouth, and anxious* point (see Figure 3).^{43, 44} The selection of *sympathetic* and *nervous subcortex* are for regulating the function of the central nervous system; *sanjian* is related to increase the metabolism of food; *liver, spleen and kidney* points are to help strengthen the energy; the mouth is also called speed recovered fatigue, and the anxious point is used to promote relaxation.^{43, 44}
- 2) Placing the seeds: After the points are located, the outer ear and the earlobe will be cleaned with 75% alcohol, then place pieces of pre-prepared tape with seeds on the participant's ear. Points on both ears will be identified and used for treatment in the proposed study.
- 3) Applying pressure on the ear points: evenly press the tape and seeds covering each ear point without rubbing (to avoid skin damage and infection at the acupuncture point) for 10 seconds per time for 3 times/point four times daily, even if they do not experience fatigue. The optimal pressure is considered to have been achieved when the participants feel localized tingling or mild discomfort.
- 4) Pressure points on the body: Participants will be asked to apply pressure using thump on the following points for fatigue and energy include outer gate point (locates between 2 tendons on the backside of the arm, free finger above the wrist) Spirit Gate or Heart 7 or Shen Men body point (locates on the wrist crease in between little finger and ring finger), large intestine 4, stomach 36, liver 3 and kidney 3. Participants will be instructed to apply pressure 10 seconds per time for 3 times/point four times daily, even if they do not experience fatigue.

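### Aim 1 compliance counts only exercise, so it cannot describe compliance with the combined exercise and acupressure program (TEHEplus)

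*Combined protocol and SAP*

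**What the plan says.** Aim 1, a primary aim, concerns the feasibility of two programs, TEHE and TEHEplus (section 2, repeated in section 7). For this aim the Analysis plan in section 7 describes eligible and recruited numbers, the number finishing the program, satisfaction and opinion, and "compliance (number of participants complete the daily step goal").

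The other statements on compliance or adherence are:

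- Section 4, feasibility paragraph: "Adherence to the intervention will be assessed using data collected from the activity tracker on minutes of moderate-intensity or greater activity".
- Section 7, opening paragraph: "Compliance with the intervention will be assessed using data collected from the activity tracker on minutes of moderate-intensity or greater activity".
- Section 7, description of the TEHE program: "Adherence to the intervention will be assessed by data collected from the activity tracker on minutes of moderate-intensity or greater activity".

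Acupressure is prescribed as a countable dose. For body points, section 7 says "Participants will be instructed to apply pressure 10 seconds per time for 3 times/point four times daily, even if they do not experience fatigue". For ear points at home, the dose is pressing "for 10 seconds per time for 3 times/point four times daily (morning, afternoon, evening and before bed"). The seeds stay on for five days and are then replaced.

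Of the Acupressure only arm, the Methods part of the abstract says "The acupressure only group will receive only instruction on how to apply the pressure on the acupressure points".

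On scope, section 4 says "This study aims to measure the feasibility of the TEHE groups (including all five intervention arms"). The matching sentence at the start of section 7 gives the number of intervention arms as three.

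**The concern.** Acupressure is what separates TEHEplus from TEHE only, and it is the part that no compliance statement counts. Followed exactly, the Aim 1 rule classes a participant who stops pressing in week 1 but keeps walking as compliant with TEHEplus. A later full-scale study would take that figure as evidence that people can sustain both parts together, which it does not show.

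There is a second, lesser consequence. Acupressure only and TEHE+MBI are compared with other arms in Aims 2 to 4. Without a record of pressing or mindfulness practice, a null result in those arms could mean that the technique does not work or that it was not used.

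**Working it through.** The plan gives no compliance figure to reproduce. The check compares what each arm is assigned with what is counted, and then bounds the effect.

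**1. Assigned against counted**

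| Arm | Assigned (abstract; section 7, interventions) | Described compliance measure |
|---|---|---|
| TEHE only | Activity and step goals | Step goal; tracker minutes |
| TEHEplus | Activity and step goals, plus acupressure | Step goal and tracker minutes, for the exercise part only |
| TEHE+MBI | Activity and step goals, plus mindfulness practice | Step goal and tracker minutes, for the exercise part only |
| Acupressure only | Acupressure | None for acupressure |

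**2. Other places where acupressure use might be recorded**

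- Ear photo (section 7, acupressure at home): its stated purpose is accurate point location. It cannot show pressing, days of wear or body points.
- Daily app survey (section 7, control group; section 8, item 5): described as covering fatigue and other symptoms. Section 9 calls the app useful for monitoring compliance but names no acupressure item.
- Week-12 open-ended questions, follow-up calls and the monthly reports of section 12: none is described as recording sessions or seed wear.
- Section 8 asks for the time and reason when the Fitbit is taken off. It asks for nothing similar when seeds are removed because of an adverse event.

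**3. Size of the uncounted dose**

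- Days: 12 weeks × 7 = 84.
- Pressing sessions: 4 per day × 84 = 336 per participant.
- Seed applications: 84 / 5 = 16.8, so about 17 per participant.

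**4. What the planned figure can say about TEHEplus**

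Let s be the proportion meeting the step goal and a the proportion adherent to acupressure. The proportion doing both lies between max(0, s + a − 1) and min(s, a). With a unmeasured it may take any value from 0 to 1, so the joint proportion lies between 0 and s.

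- In counts: if x of 22 meet the step goal, between 0 and x do both. With an assumed x = 16, the planned report is 16/22 = 72.7%, which is consistent with joint compliance from 0% to 72.7%.
- With s assumed to be 70% and a assumed to lie between 50% and 90%: the lowest value is 0.70 + 0.50 − 1 = 20% and the highest is min(0.70, 0.90) = 70%. The planned measure reports 70% throughout.

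**5. Participants concerned**

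- TEHEplus: 22 of 110 (section 7, Sample size justification), or 105 / 5 = 21 of the 105 given in the abstract, if split equally.
- All arms with an uncounted component (TEHEplus, Acupressure only, TEHE+MBI): 3 × 22 = 66 of 110, or 3 × 21 = 63 of 105. Of these, only TEHEplus is named in Aim 1.

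**The case against.** The best defence is that compliance is one item among several in a descriptive pilot. Recruitment, drop-out, completion, acceptability and tolerability are still reported by group, with satisfaction and opinion alongside. This stands. A reader might infer that Aim 1 cannot address the feasibility of TEHEplus at all, but the documents support only the narrower statement about its compliance component.

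A reader might also infer that the primary aim is compromised in both acupressure arms, 44 of 110 participants. The documents do not establish that. Aim 1 names only TEHE and TEHEplus. The section 4 sentence counts five intervention arms, but the protocol has four plus a control. The three in section 7 fits the arms that contain TEHE, which would leave Acupressure only out. The scope is unclear, so the safe statement is that this arm lacks an adherence measure for use in Aims 2 to 4.

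Nor do the documents show that no acupressure data will be collected. The full list of app items is not given, and the data collection tables omit other planned items, such as the daily survey itself. If a photo were sent at every seed change, it would be a dated record of reapplication. These points soften the claim about data. They do not alter the compliance definition, which would ignore such records if they existed.

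Finally, it is tempting to set pressing time against the 150 minutes of weekly activity cited in section 3. The documents do not support that comparison: points are tailored weekly, so the time depends on an unknown number of points, and pressing and aerobic exercise are not equal burdens.

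**Conclusion.** The concern holds for TEHEplus. Its Aim 1 compliance figure would be an exercise figure under a combined-program label, in one arm of 22 (or 21) participants, and it would leave joint compliance anywhere between zero and the reported value. Acupressure only and TEHE+MBI have the same lack of a described measure for acupressure and mindfulness, which bears on the interpretation of Aims 2 to 4.

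Severity is minor: the analysis is descriptive, the other feasibility measures are intact, and the repair is small. The conclusion rests on the compliance definitions as written and on the app survey as described. How many participants would stop acupressure cannot be calculated from the documents, and the 16 of 22 and the 50% to 90% range above are illustrations only.

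**What to change.** Add a brief item to the existing daily app survey, matched to the assigned component:

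- TEHEplus and Acupressure only: seeds on today (yes/no, with the reason if removed early), and how many of the four pressing sessions were done (0 to 4).
- TEHE+MBI: mindfulness practice done today (yes/no).

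Replace the Aim 1 compliance definition in section 7, Analysis plan, with:

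*Compliance is reported per component: daily step goal in all TEHE arms; acupressure adherence (seed-days worn and pressing sessions done, out of those prescribed) in TEHEplus and Acupressure only; mindfulness days in TEHE+MBI. In combined arms, components are reported separately and jointly using a cut-off fixed before analysis, with unanswered days shown as missing.*

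The acupressure denominators are 84 seed-days and 336 sessions. The cut-off must also say on how many days the step goal has to be met, since the plan does not.

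If no app item is added, relabel the current measure as exercise compliance and do not present it as compliance with TEHEplus.

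The cost is a few seconds a day in a survey already stated to take under 5 minutes, and one rewritten definition. No visits or participants are added. The downsides are self-report error and a possible reminder effect: the prompt may raise use in the arms that receive it and slightly affect between-arm comparisons.
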